**The project will be performed according to this protocol, relevant legislation and ICH-GCP guidelines.**

**Time plan:**

We expect to start recruiting for the project in summer 2021. Recruiting and scanning procedures are expected to be finished in summer 2024, hence the medical part of the project will end by then. The patients will be followed for 20 years after inclusion in the patient record and with questionnaires.

## Problem, aim, and hypothesis

Molecular targeting treatments and diagnostics in Prostate cancer (PCa) have evolved in recent years, while mortality from PCa has remained unchanged in Denmark (1). One molecular target is the prostate specific membrane antigen (PSMA), which is overexpressed in prostate cancer cells and can therefore serve as target for diagnosis, staging, and treatment. Positron Emission Tomography (PET) / Computed Tomography (CT) with radiolabelled PSMA (PSMA-PET/CT) has recently been implemented in the Danish Prostate Cancer guidelines (DAPROCA) as a potential tool for detecting relapsing local and metastatic disease. This decision is based on convincing studies showing a superior diagnostic accuracy of PSMA-PET/CT compared to conventional imaging in this patient setting (1).

When it comes to initial staging in primary PCa, however, there are only small diagnostic studies available performed retrospectively in heterogeneous study designs (2), and accordingly guidelines still recommend conventional imaging with contrast enhanced CT (CE-CT) and bone scintigraphy (BS) for staging in this setting(1). We believe that there is a need for larger prospective trials analyzing effects in terms of benefit for patients and society of implementing radiolabelled PSMA-PET/CT compared to conventional imaging for N-staging (lymph node metastases in the pelvic region) and M-staging (lymph node metastases outside the pelvic region, bone metastases and metastases in other organs).

The overall aim of this project is in a randomized design to compare  $^{18}\text{F}$ -PSMA-PET/CT to conventional imaging for initial staging in intermediate and high risk PCa with regard to accuracy, impact on treatment strategy and progression free survival. In a subgroup analysis we aim to analyze the added value of  $^{18}\text{F}$ -PSMA-PET/Magnetic Resonance (MR) for local staging.

We hypothesize that

- *Staging intermediate and high risk PCa with  $^{18}\text{F}$ -PSMA PET/CT and PET/MRI is more accurate at local-, N- and M-staging compared to conventional staging and therefore will lead to a change in treatment strategy with improved progression free survival.*

## Background

PCa is the most frequent cancer form in men in developed countries (3) with approximately 4,500 new cases reported annually in Denmark, 980 of which are based in the Region of Southern Denmark (RSD). The relative 5-year survival is 87% (4). The course of disease ranges from well differentiated tumors localized to the prostate gland itself, being potentially curable, to aggressive, rapidly disseminating variants with poor prognosis despite intensive treatment.

Choice of treatment regimen at primary diagnosis is based on risk stratification, staging of the disease, and general health condition of the patient (1, 5). In intermediate and high risk PCa, further staging procedures besides T-staging (6) is warranted. CE-CT or magnetic resonance (MR) is used for N-staging in cases when pelvic lymph node dissection is avoided during radical prostatectomy or when surgery is refrained from (7), although either modality has a reported sensitivity of approximately 40% (8). M-staging is traditionally obtained from BS, which reflects bone metabolism and has a reported sensitivity as well as specificity of

80% (9). An alternative modality reflecting bone metabolism is the  $^{18}\text{F}$ -sodium fluoride PET/CT (NaF-PET) which has a superior accuracy compared to BS (10, 11). BS has been substituted with NaF-PET in clinical routine at our department, and will as well in this study. Multiparametric MRI (mpMRI) of the pelvis may be performed in high-risk patients for accurate T-staging and thereby planning of resection level (R-staging) before radical prostatectomy.

The treatment regimens for different stages of PCa ranges from observation, radiation therapy, radical prostatectomy and androgen deprivation to intensive chemotherapy and experimental therapeutic regimens (1, 5). The treatment regimens are associated with a specific risk of potential adverse effects, so correct staging is paramount in order to avoid unnecessary treatment complications. Curatively intended surgery or radiation treatment followed by a surveillance program is the initial intervention for patients with localized disease.

The transmembrane protein, PSMA, is expressed in abundance on the surface of prostate cancer cells. Radiolabelled ligands targeting PSMA has been developed for use in PET/CT-scanners. The ligand PSMA-1007 can be labelled with the positron emitting isotope  $^{18}\text{F}$  (12) and is only slowly excreted through the urine as opposed to the more widely used  $^{68}\text{Ga}$ -PSMA-11 (13). The slow urinary excretion of  $^{18}\text{F}$ -PSMA-1007 poses the advantage of avoiding difficulties discriminating between excreted tracer in the urinary bladder from pathological uptake in adjacent lymph nodes. Another advantage of  $^{18}\text{F}$  labelled ligands is that they can be produced in large amounts on sites with a cyclotron whereas  $^{68}\text{Ga}$  is produced in a  $^{68}\text{Ge}/^{68}\text{Ga}$  generator with limited capacity resulting in only a limited number of scans per generator per day. Of further interest is that the molecular structure, biodistribution, and tumor uptake of  $^{18}\text{F}$ -PSMA-1007 is very similar to that of  $^{177}\text{Lu}$ -PSMA-617(12), which is a radiotherapeutic agent (14). This could provide invaluable information on dosimetry calculations as well as predictive information in a potential future theranostic approach.

The  $^{18}\text{F}$  labeled PSMA-PET/CT has so far shown detection rates of up to 94% in patients with biochemical recurrence of PCa after radical prostatectomy with curative intend (15). Several studies of the feasibility of the  $^{68}\text{Ga}$  labelled PSMA-PET/CT in various settings of PCa patients and with various endpoints have been reported (2, 16-19). These all show promising results for  $^{68}\text{Ga}$ -PSMA PET/CT but also remark upon the heterogeneous nature of the somewhat sparse data available and call for randomized controlled trials. The literature regarding  $^{18}\text{F}$ -PSMA-PET/CT for staging of primary PCa comprises only two retrospective studies with 10 and 8 patients, respectively (20, 21), both of them also focusing on the added value of combining  $^{18}\text{F}$ -PSMA-PET with mpMRI for a combined T- and N-staging.

Indeed, randomized controlled studies in well powered designs addressing patient relevant outcomes of staging primary in PCa with  $^{18}\text{F}$ -PSMA-PET/CT compared to conventional imaging are considered highly relevant. This is also highlighted in a recent international consensus report on molecular imaging and theranostics in PCa (22).

## The research medicine

The research medicine,  $^{18}\text{F}$ -PSMA, is a PET-tracer produced and applied clinically every week in the Departments of Nuclear Medicine, RSD, for the detection of relapse of PCa after curative intended therapy, hence  $^{18}\text{F}$ -PSMA is medicine we know very well. We have the license to use  $^{18}\text{F}$ -PSMA intravenously for a PET/CT scan for all cancer types expressing PSMA on the surface, as prostate cancer does. The difference in this proposed protocolled use of the drug from the current clinical use is the time point for application in the disease course. Today it is used when the patients are suspected for relaps after curatively intended therapy. In the PCa patient setting, we will use  $^{18}\text{F}$ -PSMA when the patients are newly diagnosed with PCa and not yet treated. Research shows promising results for accuracy of  $^{18}\text{F}$ -PSMA-PET/CT in this patient setting (23), but the patient benefit from being staged with PSMA-PET/CT is not yet evaluated.

The risks for the patients scanned with this drug are very discrete. We are not aware of any patients reacting allergically or with any other side effects, presumably because  $^{18}\text{F}$ -PSMA is administrated in extremely small doses, and it is not considered having any pharmacological or pharmaco-dynamic effect. We consider the risks of this medicine no larger than the medicine for conventional imaging. There will be no difference in the dose administered in our study compared with the use in clinical practice, 2 MBq pr kg. bodyweight, between 150 and 300 MBq; max. 1,8 mg PSMA and in many cases much less. The drug will be administered only once, 60 min before the scan, intravenously and in the cooperating departments by authorized personel as in the clinical setting. Paravenous injection can rarely happen with following local irritation shortly, but the medicine has a short half life in the body (< 2 hours).

Labelling, storage, compliance and destruction of the medicine is not considered a problem, as the patients are injection in the involved departments as in clinical routine. As the patients are all men, anticonception for fertile women is not relevant. As the medicine is used in very small doses, excretion in seemen is in a level where anticonception is not considered relevant for this reason.

The patients will be treated clinically following the national clinical guidelines for PCa at any time.

The project will be monitored by the local GCP-unit at OUH, part of OPEN, [[name]](#)

## Safety

We will register side effects from the  $^{18}\text{F}$ -PSMA during the 2 hours the patients are in our department after the injection. As the drug is non-detectable the next day, we expect potential side effects to show in this period – according to “the summary of product characteristics, 4.8” no adverse reactions to the medicine are reported. We will encourage the patients to contact the principal investigator if anything unusual happens during 24 hours after injection. Any suspected side effect will be registered in the REDCap database.

In case of a Serious Adverse Event they will be reported to the sponser within 24 hours from knowledge of it. The sponsor will report Suspected Unexpected Seriuos Adverse Reactions within 2 days to The Ethics Comite and the Danish Medicines Agency, as well as all principal investigators. Yearly reporting of safety and adverse events to The Ethics Comite and the Danish Medicines Agency will be performed by the sponsor.

As the medicine has the short half life in the body, the patients should be followed a maximum of 24 hours after injection. We will register the dose given in the electronic patient file as usually done in clinical practice, and it will be registered in the projects REDCap database along with the other project registrations. The medicine is well known to have no adverse effects and is only used for diagnoses. In case of reported “Serious Adverse Events” or “Suspected Unexpected Serious Adverse Reactions” related to the medicine, termination of the project will be considered.

## Research plan

The study is planned in a prospective randomized controlled design as illustrated in appendix 1 and 2 and will be carried out in close collaboration with the Department of Urology. The patients will be included and randomized as a part of one of the initial doctors appointments in a consultation room, and they will be encouraged to bring a relative to this consultation. Patients are identified when they have an appointment at Department of Urology, and the researchers will be given information from the clinicians, which means that they will not access the patient journals before enrolling. The patients will be informed about the project from the PhD-student, a physician from the Nuclear Medicine Departments, an Urologist from the cooperating departments or a nurse involved in the project, all with expertise in prostate cancer. They will be offered time to consider enrolment in the trial. The patients will be offered further information and answering of upcoming questions over the telephone after the initial talk. At this time or one of the following days, when they have accepted to be enrolled in the project and signed the written consent, they will be randomized in REDCap, where the randomisation code is kept. The randomization will be stratified according to the patients clinical risk status and pathology of biopsies. The written consents will be collected at the Nuclear Medicine Department, when they meet for their scan and at the earliest the day after the information in Department of Urology. Our study population will comprise men with a newly diagnosed intermediate or high risk (including locally advanced) PCa (1) or with a clinical suspicion of metastases based on other findings. Included patients will be randomized into a control group (A) and an interventional group (B). Group A will be staged by conventional imaging, i.e. CE-CT for N-staging and NaF-PET for M-staging. Group B will be staged by F-PSMA PET/CT for both N- and M-staging. A subset of patients with risk of extracapsular extension considered for radical prostatectomy in group B will also have an F-PSMA-PET/mpMRI-scan for T-staging (evaluation of the tumor). This scan will be performed in continuation of the F-PSMA-PET/CT, i.e. on the same administered dose of F-PSMA. Furthermore, a subgroup of patients in group B will have a blinded NaF-PET-scan for the purpose of performing comparative accuracy analyses.

Biopsy of suspected metastatic lesions in N- and M-positive patients (suspicion of metastases) as well as lymph node specimen in N- and M-negative patients will be intended as reference standard in both groups as well as a nadir unmeasurably low post-surgery prostate specific antigen blood sample to indicate no residual disease where applicable. Reference standard in the accuracy analysis of F-PSMA PET/mpMRI with regard to T- staging is histopathology on surgical specimen. As the risk of distant metastases increases with increasing PSA-levels, analyses will be performed on both population level as a whole as well as in two PSA-strata with cut-off being PSA=100 ng/ml.

Treatment and subsequent follow-up will be planned on the basis of the results of the scans and according to current guidelines (1, 5).

Follow-up data will be collected from patient journals by the researcher/principal investigator or a delegate, and will consist of clinical information, examination reports, blood test results, information about treatments and pathology reports, all performed in a clinical setup as determined by the clinician. No extra visits, scans or blood test are required except for questionnaires. The patients will be asked to fill in questionnaires (EQ-5D-5L, FACT-P and EPIC 26) concerning quality of life during at baseline and 3, 6, 12, 24, 60, 120 og 236 months after recruitment. The questionnaires will be delivered to the patients e-boks from REDCap automatically at the specific time points. All collected information will be used in this project for analysis of treatment decision, relapse detection, overall survival and quality of life in the two patient groups.

Primary endpoints (Group A vs. B)

1. Treatment strategies and progression-free survival
2. Quality of life measures

Secondary endpoints

1. Overall survival (Group A vs. B)
2.  $^{18}\text{F}$ -PSMA-PET/MR for evaluation of extension of tumor in the prostate gland and surrounding structures compared to histopathology on surgical specimen.
3. Accuracy of  $^{18}\text{F}$ -PSMA-PET/CT compared to NaF-PET/CT for evaluation of bone metastases

Four publications are planned, cf. section "Planned publications" below. Studies 1 and 4 will address the presumed patient benefit from staging with  $^{18}\text{F}$ -PSMA PET/CT in a randomized design, and outcome measures will consequently be impact on stage migration, treatment decision, progression free survival, and time to relapse in group A vs. group B. As studies 2 and 3 are comparative studies, outcome measures in this setting will be accuracy measures regarding N- and M-staging in study 2, and T- and R-staging as well as change in treatment intend in study 3.

Beyond the scope of this PhD-project we plan a follow-up time period of up to 20 years for analysis of disease free period, overall survival and quality of life.

Admittance to documents and data including patients journals are given to the relevant GCP-units and the Danish Medicines Agency for monitoring, audition and inspection of the project.

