## Sample size and statistical analyses

Assuming that staging intermediate and high risk PCa with  $^{18}\text{F}$ -PSMA PET/CT leads to upstaging in 20%, 398 patients, i.e. 199 patients in each arm, will be necessary to estimate the proportion of upstaged patients with  $^{18}\text{F}$ -PSMA PET/CT with sufficient precision as the expected length of the Wilson-score 95% CI for this proportion will be 11% (simulation study with N=2000 trials). These numbers are sufficient to indicate that the proportion of upstaged patients with  $^{18}\text{F}$ -PSMA PET/CT is statistically significantly larger than 12.9%

under above assumptions (power: 80%; two-sided testing; Type I error: 5%). A total of 448 patients (224 in each arm) are sufficient to indicate a statistically significant difference in progression free survival with assumed hazard rates of 0.35 and 0.5 for 18F-PSMA PET/CT and conventional staging respectively, implying a hazard ratio of 0.7. Estimates are based on a study duration of 4 years, consisting of 3 years accrual time and minimum follow-up period of 1 year before the first data collection, and a loss-to-follow-up of 10% (two-sample comparison of survivor functions; Exponential test; Type I error: 5%). Therefore, **448 patients (224 in each arm)** will be included in the study. For sample size calculation for the accuracy analyses planned in Group B only, we assumed a prevalence of metastases of 30%, sensitivity and specificity of 0.38 and 0.91 for conventional imaging, and 0.85 and 0.98 for PSMA-PET/CT. Then, a sample size of **128 patients** is sufficient to indicate a superior sensitivity for PSMA-PET/CT and a non-inferior specificity for PSMA-PET/CT, with a non-inferiority margin of 0.052, at a significance level of 5% (two-sided) with a power of 80%. We expect 224 patients from OUH, 80 patients from Hospital of Little Belt, 72 patients from Hospital of South West Jutland and 72 patients from Hospital Sønderjylland. Patients from Hospital Sønderjylland will have their scans performed in either Hospital of Little Belt or OUH Odense.

Primary analyses will be done as indicated in the sample size rationale above. Cox proportional hazard regressions will be adjusted for available demographic and clinical baseline variables, and graphical displays will comprise Kaplan-Meier plots including risk tables (i.e. patients at risk in each group).

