## Feasibility

Patient recruitment will be performed in collaboration with relevant departments of urology in RSD. One or more parallel PhD-projects on the same study population, but nested in the Department of Urology, OUH, is planned, thereby enabling patient recruitment on either of the two departments in close cooperation. It is considered achievable to include the required 448 patients in this setting.

The Department of Nuclear Medicine, OUH, received approval to produce  $^{18}\text{F}$ -PSMA-1007 from the Danish Medicines Agency in 2019.  $^{18}\text{F}$  will routinely be produced on our two cyclotrons, and our well-equipped radiochemistry is trained in the production and labelling of a wide variety of PET-tracers complying with Good Manufacturing Practice (GMP). The tracers will be shipped to the cooperating departments. We currently have five state-of-the-art PET/CT-scanners and a PET/MRI-scanner, and will as such have all the

prerequisites for tracer production and performing the planned scans together with the cooperating Nuclear Medicine Departments.

The PSMA-PET scans performed in OUH will be evaluated and documented as in clinical practice by the applicant and three supervisors as well as a PhD student from another PhD-project - all being Nuclear Medicine specialists along with specialists in radiology, and the same set-up is planned in the cooperating departments. Conventional scans will be evaluated as part of the daily routine at the Departments of Nuclear Medicine (NaF-PET) and Radiology (CE-CT, mpMRI). The SharePoint and RedCap systems will be used for data collection and management in line with the European data protection regulation (GDPR) implemented by May 25 2018. Sharepoint will be used for safe storage of permissions and registrations, and REDCap for patient data.

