## Appendix 1, inclusion and exclusion criteria

Inclusion criteria, all must be fulfilled	Exclusion criteria, any criterion fulfilled warrants exclusion
Has given informed consent to participate	Consent not given
Can read and understand provided patient information material in Danish	Inability to read and/or understand provided patient information material in Danish
Biopsy verified, newly diagnosed and untreated PCa	Previously given consent to this study withdrawn for any reason
Any, some, or all of the following features: 
 
• PSA <math>\geq</math> 20 ng/ml OR
 
• Gleason Score <math>\geq</math> 4+3 OR
 
• Tumor stage cT2c or above as determined by digital rectal exploration and/or transrectal ultrasonography
 
• Suspicion of metastases as judged clinically, e.g. bone pain
 
	Staging by imaging not warranted as judged clinically
Staging by imaging is warranted	Allergy towards NaF, PSMA or other contents in the solutions

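### Four hospitals recruit, but hospital is neither a randomisation factor nor a named analysis term, which costs balance and some precision but does not bias the comparison

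*Combined protocol and SAP*

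**What the plan says.** **Randomisation.** The Research plan gives one sentence on stratification: "The randomization will be stratified according to the patients clinical risk status and pathology of biopsies". It does not state the levels of either factor, a block size or an allocation method.

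**Recruitment.** Under Sample size and statistical analyses: "We expect 224 patients from OUH, 80 patients from Hospital of Little Belt, 72 patients from Hospital of South West Jutland". The fourth centre, Sønderjylland, is put down for another 72 men. On where that centre's men are scanned, the section adds: "Patients from Hospital Sønderjylland will have their scans performed in either Hospital of Little Belt or OUH Odense".

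**Analysis.** The same section says: "Cox proportional hazard regressions will be adjusted for available demographic and clinical baseline variables". The variables are not listed. Neither hospital nor the two stratification factors are named. The FACT-P paragraph names no covariates.

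**Where hospital enters the data.**
- Reading: Feasibility describes the team that reads PSMA-PET scans at OUH and says that "the same set-up is planned in the cooperating departments". Conventional scans are read in each department's daily routine. No central reading is described.
- Treatment and follow-up: under the Research plan these follow the scan results and guidelines. The local clinician decides on follow-up tests, and the trial requires no extra blood tests.
- Progression: Ethical aspects dates it at the second of two successive rising PSA values.

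**The concern.** Half of the 448 men are expected from outside OUH. A hospital's testing interval shifts its recorded progression dates, and its readers and clinicians influence stage and treatment. Treatment strategy and PFS together form the first primary endpoint, so hospital could plausibly be related to it.

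If hospital is related to outcome, leaving it out has two effects. The arms can be unevenly split within a hospital by chance, most visibly in the smaller ones. Variation between hospitals also stays in the A-versus-B comparison as unexplained variation. Because the Cox covariates are not listed, whether to add hospital would be decided after the data are in.

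**Working it through.** **1. The plan's own figure.** Inputs from the sample size section: hazards 0.5 and 0.35 (read as annual), 3 years' accrual, 4 years in total, 10% loss, exponential test, 5% type I error. Two-sided testing and 80% power are assumed for PFS, because they are stated only for the upstaging and accuracy calculations. Loss is taken as an annual rate of −ln(0.9).

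With φ(λ) = λ²/P(event), the event probabilities are 0.618 (λ = 0.5), 0.503 (λ = 0.35) and 0.565 (mean hazard, λ = 0.425):

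N = [1.960·√(4φ(0.425)) + 0.842·√(2φ(0.5) + 2φ(0.35))]² / (0.5 − 0.35)² = (1.960 × 1.130 + 0.842 × 1.138)² / 0.0225 ≈ 447.7

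This rounds to 224 per arm, or 448, so the plan's number reproduces. The recruitment forecast agrees: 224 + 80 + 72 + 72 = 448.

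**2. Chance imbalance by hospital.** Hospital is not balanced by design. The protocol gives no allocation method, so two cases are shown. The effect of stratifying on risk and pathology is ignored in both. A split of 60:40 or worse means at least 44 of 72 men, or at least 48 of 80, in either arm.

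*Totals fixed at 224 per arm (hypergeometric).*
- SD of the group B count at a 72-man hospital = √(72 × 0.25 × 376/447) = 3.89.
- SD of the arm difference = 2 × 3.89 = 7.8, so the 95% range is about ±15 men (1.96 × 7.8). The exact central range is 28 to 44 men in group B.
- P(60:40 or worse) = 0.053 for n = 72 and 0.064 for n = 80.
- Treating the three hospitals as independent: 1 − (1 − 0.053)²(1 − 0.064) = 0.16. Simulation with the joint constraint also gives 0.16.

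*Simple 1:1 allocation (binomial).*
- SD of the arm difference at a 72-man hospital = √72 = 8.5, so the 95% range is about ±17 men.
- P(60:40 or worse) = 0.076 for n = 72 and 0.093 for n = 80.
- At least one of three: 1 − (1 − 0.076)²(1 − 0.093) = 0.23.

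**3. Effect on the PFS test.** Each scenario used 4,000 simulated trials of 448 men, with control hazard 0.5, hazard ratio 0.7 (or 1 for type I error), and accrual and loss as in step 1. The tests were log-rank tests with and without stratification by hospital. The hospital hazard multipliers are assumptions, given in the order of the 224-, 80-, 72- and 72-man hospitals.

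| Multipliers | Power: hospital in neither | Power: analysis only | Power: randomisation and analysis | Type I error: hospital in neither |
|---|---|---|---|---|
| 1 / 1 / 1 / 1 | 80.5% | 79.6% | 80.9% | 4.9% |
| 1 / 1.3 / 0.7 / 1.5 | 79.3% | 81.1% | 81.9% | 5.4% |
| 1 / 2 / 0.5 / 2 | 75.5% | 81.7% | 83.6% | 5.2% |

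The simulation standard error of a power figure is about √(0.8 × 0.2/4000) = 0.6 points, so the first row shows no real difference. Comparing hospital in neither with hospital in both, the gain is 0.4, 2.6 and 8.1 points. The analysis term alone gains 1.8 and 6.2 points in the second and third rows.

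Balancing by hospital without analysing by it is not enough. In the third scenario that gave 78.1% power and 3.8% type I error.

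**4. Feasibility of more strata.** Assuming two levels for each existing factor, 4 × 2 × 2 = 16 strata, averaging 448/16 = 28 men overall and 72/4 = 18 at a 72-man hospital.

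**The case against.** The strongest reply is that the effect is small and unproven. The documents give no figures on differences between hospitals, and they say that treatment follows national guidelines, which points towards similar practice. The 8-point loss needs hospital hazards that range fourfold (0.5 to 2). The covariate list is also open, so hospital is unspecified rather than excluded. All of this stands, and it is why the point is minor. It does not remove the point: hospital is not a demographic or clinical variable on an ordinary reading, the trial already holds it, and the analysis term costs almost nothing.

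A second reply is that recruiting hospital is an imperfect stand-in for readers, because one hospital's men are scanned at two others. This also stands. The term captures local treatment and PSA testing better than it captures reading.

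Three stronger readings are tempting, and the documents do not support them.

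- *Biopsy pathology merely repeats risk status, so it could be dropped.* Appendix 1 does list "Gleason Score" beside PSA, tumour stage and suspected metastases, but that is an eligibility list, not a definition of strata. Any one feature suffices, so grade can still vary among enrolled men. The Research plan defines neither factor's levels. With about 28 men per stratum there is also no need to give up a disease factor.
- *The omission biases the result.* Randomisation makes hospital independent of arm on average, and simulated type I error stayed between 4.9% and 5.4%.
- *Hospital balance is needed to protect the PET/mpMRI subset.* That subset lies within group B and is judged against histopathology, so balance between A and B is not at issue.

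**Conclusion.** The point holds as a minor one. Recruiting hospital should be named in the analysis, and in the randomisation if that is still possible. What is lost is balance and precision: a 16% to 23% chance of at least one clearly uneven smaller hospital, depending on an allocation method the protocol does not state, and between under 1 and about 8 points of PFS power. The upper figure rests entirely on assumed hospital multipliers. If hospitals do not differ, nothing measurable is lost. The 448 is not in question, and a significant result under the present plan would not be invalid on this ground.

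**What to change.** 1. **PFS analysis:** stratify the Cox model by recruiting hospital, and state this before outcome data are examined.
2. **FACT-P analysis:** include recruiting hospital as a categorical term in the model for change from inclusion to 12 months.
3. **Definition:** state that hospital means the recruiting hospital, and that it does not fully capture reader differences, because the men from Hospital Sønderjylland are scanned elsewhere.
4. **Randomisation, only if it has not started:** add hospital as a REDCap stratification factor, keep both existing factors and write down their levels. If it has started, make the analysis changes alone. They recover most of the simulated gain.

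**Cost:** the sample size does not change. The FACT-P model gains three parameters (four hospitals less one). The stratified Cox model adds no hospital coefficients, but it compares men only within hospitals; with no hospital effect, simulated power moved by less than 1 point. Adding hospital to the randomisation multiplies the number of strata by four, which is workable at the sizes shown.
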